### **11.1.3**

#### **Dose Reductions**

Dose reductions with regards to changes in the concentrations of talimogene laherparepvec are not permitted. However, patients may require a reduction in the volume injected due to a disease response (defined in dosing section) or due to local toxicity at the injection site. However, if in the course of administration of talimogene laherparepvec the subject cannot tolerate the full dose due to an injection-related adverse event such as pain, the total volume given should be recorded, and the reason for intolerance should be documented as an adverse event.

### **11.1.4**

#### **Talimogene Laherparepvec Dosage Adjustments, Delays, Rules for Withholding or Restarting, Permanent Discontinuation**

If talimogene laherparepvec treatment was delayed by > 2 weeks, that dose will be deemed to have been missed and the subject will proceed to the next scheduled treatment visit. Dose reductions of talimogene laherparepvec is not permitted, other than a reduction in the volume injected due to a disease response.

If a subject experiences any of the following treatment-related toxicities, talimogene laherparepvec administration should be delayed until the toxicity has resolved to at least CTCAR grade 1 or baseline:

- Grade 2 or greater immune-mediated adverse events, with the exception of vitiligo
- Grade 2 or greater allergic reactions
- Any other grade 3 or greater hematologic or non-hematologic toxicity

Subjects who are receiving talimogene laherparepvec may not receive systemic antiherpetic drugs (eg, acyclovir, valacyclovir, famciclovir), but may receive a topically administered antiherpetic drug more than 20 cm from a talimogene laherparepvec injection site. Dosing should be permanently discontinued if, in the opinion of the investigator, the subject develops clinical evidence of any systemic herpes infection (such as encephalitis or disseminated infection). If the subject requires corticosteroid dosing of > 10 mg prednisone daily (or equivalent) for related toxicities, talimogene laherparepvec dosing must be withheld until the corticosteroid dose has decreased to  $\leq$  10 mg prednisone daily (or equivalent).

Talimogene laherparepvec treatment should be continued based on the potential benefit/risk assessment of the subject. If talimogene laherparepvec dosing is delayed by more than 4 weeks from the date of the planned dose (ie, approximately 6 weeks or 7 weeks depending whether the patient is receiving Q2W or Q3W dosing from the previous dose) due to the occurrence of an adverse event that is considered related to talimogene laherparepvec, the subject must be permanently withdrawn from talimogene laherparepvec treatment.

Talimogene laherparepvec is to be permanently discontinued for subjects meeting any of the following criteria:

- The subject, for any reason, requires treatment with another anticancer therapeutic agent for treatment of the study disease. In this case, discontinuation from the treatment occurs immediately upon introduction of the new agent.
- Confirmed PD
- A grade 2 or greater immune-mediated adverse event (with the exception of vitiligo) or allergic reactions attributed to talimogene laherparepvec that would require a dose delay of greater than 4 weeks from the date of the planned dose (ie, approximately 6 weeks from the previous dose).  
Note: immune-mediated glomerulonephritis, vasculitis, and pneumonitis and exacerbation of psoriasis have been observed in subjects receiving

talimogene laherparepvec in clinical trials. Most of these subjects had a history of other autoimmune disease and/or prior treatment with agents that offered plausible alternative etiologies, however, immune-mediated adverse events can potentially involve any organ system

- Any other talimogene laherparepvec-related non-hematologic or hematologic toxicities grade 3 or greater occur that, in the opinion of the investigator, would require a dose delay of greater than 4 weeks from the date of the planned dose (ie, approximately 6 weeks from the previous dose)
- The subject develops clinical evidence of any systemic herpes infection (such as encephalitis or disseminated infection)
- A female subject becomes pregnant or fails to use acceptable method(s) of affective contraception (for those subjects who are able to conceive)
- Concurrent medical illness that, in the judgment of the investigator, would make continued treatment with talimogene laherparepvec dangerous for the subject

For additional information related to special warnings and precautions for the use of talimogene laherparepvec, please refer to the latest version of the Investigator's Brochure.

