### **6.2 Subject Exclusion Criteria**

- Active herpetic skin lesions or prior complications of HSV-1 infection (such as herpetic keratitis, herpetic encephalitis)
- Receipt of a therapeutic anticoagulant
- Receipt of live vaccine within 28 days of planned first dose of TVEC

- Receipt of another cancer therapy (targeted therapy, chemotherapy, investigational therapy, immunotherapy, radiotherapy or surgery) which is yielding an overall response (by response criteria in this study)
  - Patients with stable or progressing disease (as determined by at least 2 consecutive assessments at 6-week interval) can continue to receive the same therapy during treatment as part of this protocol
- History of symptomatic autoimmune disease (such as lupus, scleroderma, Crohn's disease, ulcerative colitis) requiring systemic treatment (for example corticosteroids or immunosuppressants); replacement therapy (for example, thyroxine, insulin) is not considered a systemic treatment
- History of high grade (CTCAE  $\geq$  Grade 3) immune mediated adverse event from prior cancer immunotherapy
- History of CTCAE  $\geq$  Grade 2 immune mediated endocrinopathy from prior cancer immunotherapy
- Intermittent or chronic use of oral or intravenous antiherpetic drug (such as acyclovir)
- Active or chronic hepatitis B or C infection
  - Previously infected with evidence of immunity and no evidence of active hepatitis is not an exclusion criterion
- Known human immunodeficiency virus (HIV) infection
- Known leukemia or lymphoma
- Common variable immunodeficiency
- Patients requiring chronic high dose immunosuppressants including steroids (prednisone daily equivalent of  $\geq$  10 mg)
- Known severe congenital or acquired cellular or humoral immunodeficient or immunocompromised patients (as noted in Investigators Brochure and Developmental Core Safety Information)
- High likelihood of protocol non-compliance (in opinion of investigator)
- Woman of childbearing potential unwilling to use effective contraception during protocol treatment and for 3 months after last dose of Talimogene Laherparepvec
- Woman of childbearing potential that is pregnant or breast-feeding, or planning to become pregnant or breast-feed during protocol treatment and for 3 months after last dose of Talimogene Laherparepvec

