## **9.1 Oncolytic immunotherapy by Talimogene Laherparepvec (TALIMOGENE LAHERPAREPVEC) administration**

Intralesional administration of Talimogene Laherparepvec will be performed in a private room in the outpatient clinic area.

Intralesional therapy for cutaneous metastasis is a standard procedure, but Talimogene Laherparepvec is an investigational agent.

The selection of cutaneous metastasis for Talimogene Laherparepvec injection will be based on lesion size. Injections will begin with the largest metastasis, and then will proceed to the next largest metastasis, until all the cutaneous metastases have been injected, or the maximum volume of Talimogene Laherparepvec (4 mL) has been used for that treatment cycle. The injection of all of the cutaneous metastases is expected to take no more than 20 minutes.

Visceral metastases will not be injected with Talimogene Laherparepvec during the protocol therapy.

During the course of Talimogene Laherparepvec administration, patients will be clinically evaluated every 2-3 weeks (as indicated in section 10.0), for any symptoms or signs of toxicity. If a patient experiences a grade 2 or higher immune mediated adverse event, Talimogene Laherparepvec administration will be delayed until the adverse event is grade 1 or less in severity. Non-immune related adverse events grade 3 or greater will also lead to a delay in Talimogene Laherparepvec administration, until they have resolved to grade 1 or less. In the event of a dose limiting toxicity, as described in section 11.1.3, Talimogene Laherparepvec administration will be discontinued indefinitely.

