The first dose of radiation will be delivered 6 (+/- 2) hours after the second dose of Talimogene Laherparepvec. Preclinical studies have demonstrated this sequence of therapy and interval of time is necessary to yield synergistic effects of oncolytic immunotherapy and radiotherapy. The subsequent two doses of radiation therapy will occur every 3-6 days, over no more than 14 days.

During the course of radiation therapy patients will be clinically evaluated at least once a week, for any symptoms or signs of toxicity.

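### The only T-VEC hold tied to steroid dose covers steroids given for related toxicities, so the protocol text allows dosing during high dose steroids given for other reasons

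*Combined protocol and SAP*

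**What the plan says.** Section 11.1.4 contains the only on-study rule that links a hold to steroid dose. It begins "If the subject requires corticosteroid dosing of > 10 mg prednisone daily (or equivalent) for related toxicities" and requires dosing to be withheld until the dose is back to 10 mg or less.

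Section 9.1 has a second mandatory rule, based on event grade. For immune mediated events of grade 2 or higher, "Talimogene Laherparepvec administration will be delayed until the adverse event is grade 1 or less in severity". For other events, "Non-immune related adverse events grade 3 or greater will also lead to a delay in Talimogene Laherparepvec administration, until they have resolved" to the same grade. Neither sentence asks whether the event is related to T-VEC, and neither mentions steroid dose.

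At entry, section 6.2 excludes "Patients requiring chronic high dose immunosuppressants including steroids (prednisone daily equivalent of" 10 mg or more), with no condition on why the drug is given. A further exclusion covers known severe congenital or acquired immunodeficiency or immunocompromise. Section 6.2 also lets patients whose disease is stable or progressing on another cancer therapy continue it: they "can continue to receive the same therapy during treatment as part of this protocol".

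Among the important potential risks, section 11.1.1.1 lists disseminated herpetic infection in immunocompromised patients, and its examples include those needing high dose steroids or other immunosuppressive agents. The identified risk in section 11.1.1.0 is narrower and concerns severely immunocompromised individuals.

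**The concern.** T-VEC is a modified herpes simplex virus that replicates. The risk named in section 11.1.1.1 depends on the patient's immune state, and the reason for the steroid does not alter that state. A hold that depends on attribution is therefore narrower than the risk it guards against. The entry criterion in section 6.2 has no such limit, and section 11.1.4 itself uses reason-neutral wording for stopping T-VEC when another anticancer agent is needed.

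Unrelated steroid use is foreseeable here. Patients may be on another cancer therapy, including immunotherapy. Section 11.1.4 also notes that most subjects with the immune mediated events seen in earlier T-VEC trials had an autoimmune history or prior agents that offered another plausible cause. An investigator could reasonably judge such an event unrelated, and the steroid hold would then not apply.

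Antiviral cover is not a way round this while dosing continues, because section 11.1.4 bars systemic antiherpetic drugs in patients receiving T-VEC. What is at stake is patient safety. No endpoint, sample size or error rate depends on it.

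**Working it through.** The plan states no figure to reproduce. The check compares the rules and asks which situations each one reaches.

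| Rule | Trigger | Attribution needed? | Dosing resumes when |
|---|---|---|---|
| 11.1.4, steroid hold | Prednisone equivalent above 10 mg daily | Yes, related toxicity | Dose is 10 mg or less |
| 11.1.4, toxicity delay | Grade 2+ immune mediated (except vitiligo) or allergic; other grade 3+ | Yes, treatment-related | Grade 1 or baseline |
| 9.1, delay | Grade 2+ immune mediated; other grade 3+ | No | Grade 1 or less |

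Applying these rules:

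1. *Related event, steroids above 10 mg.* Both the 9.1 delay and the 11.1.4 steroid hold apply. Read together, they require grade 1 or less and 10 mg or less before dosing resumes. There is no gap.
2. *Unrelated event at a triggering grade.* Section 9.1 stops dosing. There is no gap while the event stays above grade 1.
3. *The same event at grade 1, taper still above 10 mg.* Section 9.1 has released and the steroid hold never applied. No mandatory hold remains.
4. *Steroids above 10 mg for a condition that never met the 9.1 trigger*, such as an unrelated non-immune event of grade 2 or lower. Neither rule applies, so there is no mandatory hold.

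The remaining provisions do not clearly cover cases 3 and 4. Continuation on benefit and risk and discontinuation for a dangerous concurrent illness (both 11.1.4), and safety withdrawal (13.0), rest on judgment and set no dose threshold. Section 13.0 does require removal of a patient found ineligible, but explains this as a change in diagnosis. The two exclusions it might bring in concern chronic high dose use and known severe immunocompromise. A short course or a taper is not clearly either.

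*Size.* The documents give no frequency, so the following are illustrations on assumed inputs. Let p be the share of patients who fall in case 3 or 4, with n = 34 (the planned maximum). Expected number = n × p; chance of at least one = 1 − (1 − p)^n.

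- p = 0.02: 34 × 0.02 = 0.68; 1 − 0.98^34 = 0.497
- p = 0.05: 34 × 0.05 = 1.70; 1 − 0.95^34 = 0.825
- p = 0.10: 34 × 0.10 = 3.40; 1 − 0.90^34 = 0.972

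With the minimum of 18 patients, the expected numbers are 0.36, 0.90 and 1.80. For one affected patient, assume 2 to 6 weeks above the threshold. With a dose every 2 weeks, that is 2/2 = 1 to 6/2 = 3 of the 8 scheduled doses, if no clinician holds them. These figures count possible dosing during high dose steroids. They do not count infections.

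**The case against.** The strongest reply is that the protocol text is not the whole rule set. Section 11.1 sends the reader to the Investigator's Brochure, the Developmental Core Safety Information and the Toxicity Management Guidelines, and section 11.1.4 refers to the Brochure again for warnings and precautions. None of these was available, and any of them may contain a hold for steroids given for any reason. This stands. A reader might infer that the trial has no broader rule anywhere; the documents show only that the protocol text has none.

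Second, the steroid sentence does not say what the toxicity must be related to. The delay list in the same section speaks of treatment, and section 11.0 grades toxicity from both oncolytic immunotherapy and radiotherapy. Steroids for radiation toxicity may already be covered. An immune event on T-VEC plus another immunotherapy may also be judged related. Both points narrow the gap without closing it.

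Third, few patients should be exposed. Entry is barred for grade 3 or higher "immune mediated adverse event from prior cancer immunotherapy" and for grade 2 or higher "immune mediated endocrinopathy from prior cancer immunotherapy", as well as for autoimmune disease needing systemic treatment. Patients continuing another therapy must already have had at least two consecutive assessments, at a 6-week interval, showing stable or progressing disease. Patients are also seen every 2 to 3 weeks, and investigators can stop dosing on judgment. This supports a low priority, but judgment remains a weaker safeguard than the fixed 10 mg limit already used for related toxicity.

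Two further readings go too far. One is that unrelated events leave T-VEC dosing unchecked; section 9.1 stops dosing for them at the stated grades. The other is that the lack of a hold for non-steroid immunosuppressants is an equally clear defect. Section 11.1.1.1 does name such agents, but permitted concurrent therapy includes chemotherapy, so a hold would need exemptions by reason for prescribing that are open to debate.

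**Conclusion.** The concern holds for the protocol text. The only mandatory hold tied to steroid dose depends on attribution, and the attribution-neutral delay in section 9.1 ends without regard to steroid dose. T-VEC may then be given during high dose steroids for an unrelated event or another condition, which is a risk state the protocol itself names.

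The likely number of patients is small, and any figure rests on assumption. The risk is listed as potential, and nothing in the documents supports a predicted number of infections. The conclusion also depends on there being no broader rule in the cited safety documents. This is a cheap improvement to patient safety and leaves the efficacy analysis as it is.

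**What to change.** - In section 11.1.4, apply the steroid hold to prednisone equivalent above 10 mg daily given *for any reason*, in place of the limit to related toxicities. Exempt brief steroid premedication for concurrent therapy that section 6.2 permits.
- In section 9.1, state that dosing resumes only when the event is grade 1 or less and the steroid dose is 10 mg or less.
- If the Investigator's Brochure, Developmental Core Safety Information or Toxicity Management Guidelines already contain such a rule, citing it in section 11.1.4 would serve the same purpose.
- Optionally, the sponsor may consider whether to extend the hold to non-steroid immunosuppressants started on study.

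The cost is a few sentences and possibly a few delayed or missed doses, since section 11.1.4 counts a dose delayed by more than 2 weeks as missed. A hold for an unrelated condition would not trigger the permanent withdrawal for long delays, which is limited to adverse events considered related to T-VEC. In Arm A, a hold at week 3 would also move the first radiotherapy fraction, which is timed 6 (±2) "hours after the second dose of Talimogene Laherparepvec"; existing holds already have this effect. Evaluability for the primary endpoint is unlikely to suffer: section 12.0 asks for one T-VEC dose, one radiotherapy dose in Arm A, a baseline assessment and at least one later assessment.

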## **11.2 Side effects of radiation therapy for cutaneous metastasis are listed below.**

Common Terminology Criteria Adverse Event	Grade 1 frequency	Grade 2 frequency	Grade 3 frequency	Grade 4 frequency
Radiation dermatitis	100%	50%	10%	<2%
Pruritis	50%	10%		
Pain of skin	50%	10%	<2%	
Skin ulceration	50%	10%	<2%	
Alopecia	100%	10%		
Skin hyperpigmentation	50%	10%	<2%	
Skin hypopigmentation	100%	10%		
Telangiectasia	50%	10%		
Skin atrophy	100%	10%	<2%	
Skin induration	100%	10%	<2%	

## **12.0 CRITERIA FOR THERAPEUTIC RESPONSE/OUTCOME ASSESSMENT**

The primary endpoint for systemic efficacy is the week 16 response of the largest metastasis not injected with Talimogene Laherparepvec or irradiated. Overall subject level response is defined as partial or complete (>50% or greater decrease in largest lesion) by the modified World Health Organization (mWHO) criteria, and will include measurements of tumor size by CT component of PET/CT, by standard uptake value (SUV) by PET component of PET/CT, and clinically by digital photography. Please see Appendix A for complete radiographic assessment details and the mWHO response criteria.

Study radiologists will be specifically informed which lesion is the target for response assessment. A separate calculation of response within and outside the irradiated volume will be determined. Study radiologists will be blinded, however, as to which treatment arm the patient has been assigned.

Radiographic imaging evaluations are considered standard of care for patients treated for cutaneous metastases.

Patients are considered evaluable for the primary endpoint if they:

- Receive one dose of Talimogene Laherparepvec, and for patients enrolled on Arm A, one dose of RT, as well as a baseline and at least one post-baseline disease assessment
- Discontinue the study due to symptomatic progression, death, or toxicity at any point, even if they have not received one dose of Talimogene Laherparepvec and one dose of RT

Patients who discontinue the study and do not meet evaluable criteria above are replaceable. In this event, the replacement patient will be assigned to the same treatment arm that lost a patient.

Patient reported health-related quality of life outcomes will be assessed using the Skindex-16 (Appendix B). The Skindex-16 is a 1 page instrument consisting of 16 items with responses provided on a 7-point Likert scale based on experience over the last week. Responses are categorized in 3 subscales: emotions, functioning, and symptoms, with combined subscale scores yielding an overall score ranging from 0 (best) to 100 (worst). Of the 16 items in the instrument, 7 contribute to symptoms, 4 contribute to emotion, and 5 contribute to functioning. In a psychometric analysis, subscales have a high degree of internal consistency reliability (Cronbach's alpha = 0.86, 0.93, 0.92 for symptoms, emotions and functioning). The subscale scores were also highly reproducible after 72 hours ( $r= 0.90, 0.89, \text{ and } 0.88$  for symptoms, emotions and functioning) (Chren MM J Cutan Med Surg 2001).

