## **9.0 TREATMENT/INTERVENTION PLAN**

### **Study Assessments and Procedures**

#### **During Treatment**

Weeks 0, 3, 5, 7, 11 and 15 ( $\pm$  1 week)

- Physical examination
- ECOG performance status
- Vital signs (weight, heart rate, blood pressure, respiratory rate, oxygen saturation) will be assessed in clinic
- Complete blood count (CBC)
- Basic metabolic profile (BMP)
- Prothrombin and activated partial thromboplastin time test (PT&APTT)
- Pregnancy test for women of childbearing potential, by blood or urine (at weeks 3, 7, 11 and 15 only)
- Research blood test
- Research skin tumor biopsy (at weeks 0, 7 and 15 only)

Weeks 0-15 ( $\pm$  1 week)

- Administration of Talimogene Laherparepvec (T-VEC)  
*\* Patients with potential for clinical benefit may continue TALIMOGENE LAHERPAREPVEC after week 15 every 2 weeks for up to 24 weeks (to be determined by treating clinician)*
- Radiation therapy for patients randomized into Arm A; first fraction given 6 (+/-2) hours after week 3 Talimogene Laherparepvec administration; 2nd and 3rd fraction given every 3-6 days over next 14 days
- Adverse event review (including NCI PRO-CTCAE v1.0, Appendix C)

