## **End of Treatment**

Week 16 ( $\pm$  1 week) or when TVEC is discontinued prior to week 15

- Physical examination
- ECOG performance status
- Vital signs (weight, heart rate, blood pressure, respiratory rate, oxygen saturation) will be assessed in clinic
- Adverse event review (including NCI PRO-CTCAE v1.0, Appendix C)
- Complete blood count (CBC)
- Comprehensive metabolic profile (CMP)
- Prothrombin and activated partial thromboplastin time test (PT&APTT)
- Research blood test (If TVEC stopped before week 15)
- Pregnancy test for women of childbearing potential (by either blood or urine)
- Research skin tumor biopsy (If TVEC stopped before week 15)
- Quality of life assessment (Skindex-16, Appendix B) to be completed by subjects
- Digital photography
- PET/CT (IV or oral contrast is not required, but is permissible if clinically indicated.)

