## 10.0 EVALUATION DURING TREATMENT/INTERVENTION

Study Timeline	Pre-Treatment	Treatment									End of Treatment 	Follow-Up 
		0 (1)	3 (1)	5 (1)	7 (1) 	9 (1)	11 (1)	13 (1)	15 (1)	16 (1)		
Week (+/-)	-4 to 0											
Assessments												
Pathology Review	X											
PET/CT (with or without contrast)	X									X		
Quality of life questionnaires	X									X		
Digital photography	X									X		
Adverse event		X	X	X	X	X	X	X	X	X		X

review 											
ECOG performance status	X	X	X	X	X		X		X	X	
Vital signs (weight, heart rate, blood pressure, respiratory rate, oxygen saturation)	X	X	X	X	X		X		X	X	
Physical exam	X	X	X	X	X		X		X	X	
Complete medical history	X										
Hepatitis B Surface Antigen, Hepatitis B Core Antibody (total), hepatitis B surface Antibody, Hepatitis C Antibody 	X										
Comprehensive metabolic profile	X									X	
Basic metabolic profile		X	X	X	X		X		X		
Complete blood count	X	X	X	X	X		X		X		
PT&APTT	X	X	X	X	X		X		X		
Pregnancy testing (blood or urine); WOCBP only	X 		X		X		X		X		
Research blood test 		X	X	X	X		X		X		
Research skin punch biopsy 		X			X				X		
Treatment											
TALIMOGENE LAHERPAREPVEC		X	X	X	X	X	X	X	X†		
Radiation therapy			X*								

†Patients with potential for clinical benefit may continue TALIMOGENE LAHERPAREPVEC after week 15 every 2 weeks for up to 24 weeks (as determined by treating clinician)

\*Only for Arm A; first fraction given 6 (+/- 2) hours after week 3 TALIMOGENE LAHERPAREPVEC administration; 2nd and 3rd fraction given every 3-6 days over no more than 14 days

Including Appendix C, "NCI PRO-CTCAE v1.0"

Within 2 weeks of starting Talimogene Laherparepvec treatment

 Research bloods will be 3 tubes (3 CPT) at each time point; stored at immune monitoring core facility for up to 1 year after completion of study

One lavender top (EDTA) tube of blood will be drawn on the same day as the research skin punch biopsy; window for biopsy will be +/- 3 weeks

Additional testing to evaluate for hepatitis maybe required depending on the serological results

For patients that discontinue TVEC before week 16, the End of Treatment visit occurs after last dose of TVEC

Follow-Up at week 20 or 4 weeks after last TVEC dose

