Note that in the above, all patients are assumed evaluable. However, it might happen that some patients are not evaluable due to various reasons such as withdrawal or loss to follow-up, etc. Such inevaluable patients will be replaced. We expect that about 13% of patients might need to be replaced. In other words, we expect to enroll up to 34 patients in total. The clinical efficacy of Talimogene Laherparepvec will be measured by the ORR and summarized by the sample proportion for each of the two arms. A comparison will be done between the two arms. Safety of Talimogene Laherparepvec will be summarized and compared similarly. QOL total and subscale scores will be summarized numerically and graphically, and trends will be observed and reported per arm. Wilcoxon rank sum tests will also be used to compare the QOL scores between the two arms for each assessment time point. DOR will be assessed using actuarial curves based on patients who achieved response and compared between the two arms using a stratified log-rank test. Time to response onset, progression free and overall survival will be analyzed in a similar way but will be based on all patients. Immunologic response data will be summarized descriptively, with mean, median and standard deviations calculated.

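### Evaluability requires a radiotherapy dose in Arm A only, so a few early leavers could count in Arm B but be replaced in Arm A; an all-randomised sensitivity analysis would show whether the preferred arm depends on this

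*Combined protocol and SAP*

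**What the plan says.** Section 12.0 gives two routes to being evaluable for the primary endpoint.

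- Route 1: the patient must "Receive one dose of Talimogene Laherparepvec, and for patients enrolled on Arm A, one dose of RT", and have a baseline and at least one post-baseline disease assessment.
- Route 2: the patient must "Discontinue the study due to symptomatic progression, death, or toxicity at any point", even without a dose of either treatment. This route is the same in both arms.

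On replacement, Section 12.0 states: "Patients who discontinue the study and do not meet evaluable criteria above are replaceable". It continues: "In this event, the replacement patient will be assigned to the same treatment arm that lost a patient". Section 14.0, after mentioning withdrawal and loss to follow-up, states: "Such inevaluable patients will be replaced".

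On timing, Section 9.0 has the "first fraction given 6 (+/-2) hours after week 3 Talimogene Laherparepvec administration". The End of Treatment visit, which includes PET/CT, takes place at week 16 "or when TVEC is discontinued prior to week 15". A footnote in Section 10.0 adds: "For patients that discontinue TVEC before week 16, the End of Treatment visit occurs after last dose of TVEC".

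Section 14.0 tests each arm with a two-stage rule: 9 evaluable patients, closing the arm if none responds, then 15, passing with 3 or more responses. If both arms pass, the one with the higher observed rate becomes the preferred treatment. No margin is set, and no analysis of the primary endpoint in all randomised patients is specified.

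**The concern.** The radiotherapy condition depends on something that happens after randomisation and can apply in one arm only. Sections 11.1.4 and 13.0 list reasons for stopping that Route 2 does not automatically cover, such as withdrawn consent, later-found ineligibility, concurrent illness, pregnancy or a switch to another anticancer agent. Suppose a patient receives the week 0 injection, leaves the study for such a reason before the first radiotherapy, and has the early-stop PET/CT. In Arm B that patient takes one of the 15 places, probably as a non-responder. In Arm A the place goes to someone else.

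An Arm A patient who stays on study but never receives radiotherapy also fails Route 1, whatever the week 16 scan shows. Arm B has no counterpart.

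At stake is the choice between arms. With 15 patients per arm and no margin, removing likely non-responders from one arm only can move that choice.

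**Working it through.** **Inputs.** From Section 14.0: 9 then 15 evaluable patients per arm; close at 0/9; pass at 3 or more of 15; response rates of 7.5% and 27%; about 13% replaced, up to 34 enrolled. From Section 2.0: response onset in earlier studies of the injection alone ranged from 1.2 to 16.9 months. Assumed, because the documents do not give it: how often the patient described above occurs, and that this patient does not respond.

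**1. The plan's own figures.** Let X be the stage 1 responses, binomial(9, p), and Y the stage 2 responses, binomial(6, p).

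- P(early stop) = (1 − p)^9 = 0.496 at 7.5% and 0.059 at 27% (stated 0.50 and 0.06).
- P(pass) = P(X ≥ 1 and X + Y ≥ 3) = 0.094 at 7.5% and 0.802 at 27%, within the stated error limits of 0.10 and 0.20.
- P(pick an arm) = P(it alone passes) + P(both pass and it has strictly more responses). For the better arm this gives 0.608, 0.715, 0.803, 0.538, 0.651, 0.539, 0.648 and 0.745, against the plan's 0.61, 0.72, 0.80, 0.54, 0.65, 0.54, 0.65 and 0.74.
- Enrolment: 30 × 1.13 = 33.9, hence 34, or about 4 replacements in the whole trial.

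The stated design figures reproduce. They assume that every patient is evaluable, as Section 14.0 says.

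**2. Why such a patient would probably be a non-responder.** The earliest quoted onset is 1.2 months: 1.2 × 30.44 / 7 = 5.2 weeks. The first radiotherapy is planned at week 3 (± 1 week), so a scan taken on stopping before then would usually come too early to show a response.

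**3. Effect on selection, 27% true rate in both arms.** Arm A stays at 27% because these patients are replaced.

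- *No such patient:* 0.411 for A and 0.411 for B; both pass with equal counts in 0.140; neither passes in 0.039.
- *A share q = 2% of patients:* the Arm B rate becomes 0.27 × (1 − 0.02) = 0.2646. P(pass) in B is 0.789; selection is 0.423 v 0.397.
- *q = 5%:* the Arm B rate becomes 0.27 × 0.95 = 0.2565. P(pass) in B is 0.769; selection is 0.441 v 0.376.
- *Severe case, one per arm:* Arm B has 14 patients at 27% plus one certain non-responder placed at random, so in stage 1 with probability 9/15. P(pass) in B is 0.760; selection is 0.451 v 0.36.

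**4. If Arm B is truly better (35% v 27%).** P(pick B) is 0.608 with no such patient and 0.554 in the severe case.

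**The case against.** The strongest reply is that the plan already deals with the main risk. Route 2 keeps progression, death and toxicity in the denominator of both arms, so Arm A cannot shed its early clinical failures. What is left is narrow: a patient with the week 0 injection, a stop for some other reason within about three weeks, and a scan all the same. Section 14.0 names withdrawal and loss to follow-up as the expected reasons for replacement. Many such patients will have no scan, and then both arms replace them. The severe case uses 2 of the roughly 4 replacements planned for the whole trial. Requiring one dose of the assigned combination is also a common choice, because it fixes what Arm A estimates. All of this stands, and it makes the point minor.

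Three stronger readings are tempting.

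- A reader might infer that the selection is biased toward Arm A. The documents do not show this: they give no rate for such patients, and the tilt vanishes if none occur or if they respond as often as the others.
- A reader might infer that one patient often decides the choice, because the two counts will often be close. Closeness does not measure impact: replacing a non-responder changes the Arm A count only if the replacement responds, which at the design rate happens 27% of the time.
- A reader might infer that the type I error exceeds 0.10. That would follow only if the 7.5% benchmark refers to all treated patients, which the documents do not say.

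Nor do the remaining wording differences amount to contradictions. The replacement sentence in Section 14.0 refers mainly to patients who have left, which fits Section 12.0. Same-arm replacement is stated in Section 12.0 even though Section 15.2 does not repeat it.

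**Conclusion.** The evaluable set is defined differently in the two arms, and no specified analysis would show whether the preferred arm depends on that. What survives the objection is a possible slight tilt toward Arm A, not an established bias. Its size rests on two assumptions: how many such patients occur, and that they are mostly non-responders. Over the range examined, the gap between the arms' chances of selection at equal 27% rates runs from zero (none), through about 2.6 points (0.423 − 0.397, at 2%), to about 9 points (0.45 − 0.36, one per arm). This does not call the two-stage rule or the sample size into question. It is a low-cost improvement, not a defect that invalidates the design.

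**What to change.** Keep the evaluable primary analysis, the 9 and 15 patient cut-offs and the ceiling of 34.

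**Section 14.0, add:**

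- A sensitivity analysis of the primary endpoint in all randomised patients, including replacements, by assigned arm. Anyone without a week 16 assessment counts as a non-responder in both arms.
- Each arm's response rate with an exact confidence interval, and a statement of whether the preferred arm is the same as in the evaluable analysis. If it differs, report the selection as not robust.
- A statement that this analysis is not used to break ties.
- A report of replacements by arm, by reason, and by whether they came before the first radiotherapy.

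**Optional wording:** cross-refer Section 15.2 to the same-arm replacement rule in Section 12.0; reconcile the progression wording of Sections 12.0 and 13.0; and reconcile the replacement wording of Sections 12.0 and 14.0, so that it is clear what happens to an Arm A patient who stays on study without radiotherapy.

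**Cost:** a few sentences, one small analysis and one table; no extra patients. The sensitivity rates will be slightly lower: 4/15 (26.7%) becomes 4/16 (25.0%) with one replaced non-responder. At equal response counts the arm with more replacements gets the lower rate. Both arms pass with equal counts in about 14% of trials at 27% each, so the analysis should test robustness only.
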